5.3. Schema

Not Applicable.

5.4. Lifestyle Requirements

Not applicable.

5.5. Screen Failures

Screen failures are defined as participants who consent to participate in the clinical study but are not subsequently entered in the study. A minimal set of screen failure information is required to ensure transparent reporting of screen failure participants to meet the Consolidated Standards of Reporting Trials (CONSORT) publishing requirements and to

respond to queries from regulatory authorities. Minimal information includes screen failure details such as demography, eligibility criteria, and any SAE. Individuals who do not meet the criteria for participation in this study (screen failure) will be recorded as a screen failure but may be rescreened at a later date. Rescreened participants will be assigned a new screening number. Pfizer approval must be provided prior to re-screening a participant.

6. STUDY INTERVENTION

Not applicable.

6.1. Participant Compliance

Not applicable.

6.2. Study Intervention

No study treatment is administered. For the purposes of this protocol, study intervention refers to requirement for scintigraphy and biological specimens.

6.3. Study Intervention Storage

Not applicable.

6.4. Measures to Minimize Bias: Randomization and Blinding

Not applicable.

6.5. Study Intervention Accountability

Not applicable.

6.6. Concomitant Treatment(s)

Not applicable.

7. PARTICIPANT DISCONTINUATION/WITHDRAWAL

7.1. Discontinuation of Study Intervention

Not applicable.

7.2. Participant Discontinuation/Withdrawal from the Study and Vital Status Follow-up

A participant may withdraw from the study at any time at his/her own request. Reasons for discontinuation from the study include *but are not limited to* the following:

- Refused further follow-up;
- Lost to follow-up;
- Death;

- Study terminated by sponsor.

Due to assessment of vital status at the Follow-Up 2 Visit, a Release of Medical Information Form will be required of all participants for the purpose of access to medical records as well as for obtaining vital status follow-up with the participant's primary physician or with death registries. The signing of this Release of Medical Information Form is in addition to the Informed Consent Document. In some cases, sites may combine these 2 forms into a single form, as is their standard practice.

Participants should be questioned regarding their reason for withdrawal. A Follow-Up 2 Visit should be performed for those participants with ATTR-CM if consent has been obtained. The participant will be permanently discontinued from the study at that time.

If a participant withdraws from the study, he/she may request destruction of any remaining samples taken and not tested, and the investigator must document any such requests in the site study records and notify the sponsor accordingly. If the participant withdraws from the study and also withdraws consent (see below) for disclosure of future information, no further evaluations should be performed, and no additional data should be collected. The sponsor may retain and continue to use any data collected before such withdrawal of consent.

Lack of completion of all or any of the withdrawal/early termination procedures will not be viewed as protocol deviations so long as the participant's safety was preserved.

7.3. Withdrawal of Consent:

Participants who request to discontinue study participation must continue to be followed for protocol-specified follow-up procedures. The only exception to this is when a participant specifically withdraws consent for any further contact with him or her or persons previously authorized by the participant to provide this information. Participants should notify the investigator in writing of the decision to withdraw consent from future follow-up, whenever possible. The withdrawal of consent should be explained in detail in the medical records by the investigator, as to whether the withdrawal is only from study procedures and/or study follow-up and entered on the appropriate case report form (CRF) page. In the event that vital status (whether the participant is alive or dead) is being measured, publicly available information should be used to determine vital status only as appropriately directed in accordance with local law.

7.4. Lost to Follow-up

A participant will be considered lost to follow-up if he or she repeatedly fails to return for scheduled visits and is unable to be contacted by the study site.

The following actions must be taken if a participant fails to return for a required study visit:

- The site must attempt to contact the participant and reschedule the missed visit as soon as possible and counsel the participant on the importance of maintaining the assigned visit schedule and ascertain whether or not the participant wishes to and/or should continue in the study.

- Before a participant is deemed lost to follow-up, the investigator or designee must make every effort to regain contact with the participant (where possible, 3 telephone calls and, if necessary, a certified letter to the participant's last known mailing address or local equivalent methods). These contact attempts should be documented in the participant's medical record.
- Should the participant continue to be unreachable, he/she will be considered to have withdrawn from the study.

Discontinuation of specific sites or of the study as a whole is handled as part of [Section 10.1.6](#).

8. STUDY ASSESSMENTS AND PROCEDURES

8.1. Procedures

The investigator (or an appropriate delegate at the investigator site) must obtain a signed and dated ICD before performing any study-specific procedures.

Study procedures and their timing are summarized in the [SoA](#). Protocol waivers or exemptions are not allowed.

Safety issues should be discussed with the sponsor immediately upon occurrence or awareness to determine if the participant in the study should continue.

Adherence to the study design requirements, including those specified in the [SoA](#), is essential and required for study conduct.

All screening evaluations must be completed and reviewed to confirm that potential participants meet all eligibility criteria. The investigator will maintain a screening log to record details of all participants screened and to confirm eligibility or record reasons for screening failure, as applicable.

For samples being collected and shipped, detailed collection, processing, storage, and shipment instructions and contact information will be provided to the investigator site prior to initiation of the study.

The total blood sampling volume for individual participants in this study is approximately 63 mL. The actual collection times of blood sampling may change. Additional blood samples may be taken for safety assessments at times specified by Pfizer, provided the total volume taken during the study does not exceed 550 mL during any period of 60 consecutive days.

Protocol-specified safety laboratory tests may be performed at a local laboratory if the study participant is unable to visit the study site, where allowable by law or local guidance. Local laboratory reference ranges need to be documented.

8.1.1. Screening Visit

The following procedures will be conducted during the Screening visit. Details of the assessments are located in [Section 8.2](#):

- Informed consent.
- All inclusion and exclusion criteria will be reviewed to ensure eligibility for participation in this study.
- Echocardiography (unless obtained within 6 months prior to Screening Visit and results are available).
- Complete medical history.
- Measure vital signs (systolic and diastolic blood pressure supine and standing and pulse rate supine and standing).
- Demography (date of birth, age, gender, race and ethnicity).
- Full physical examination including weight and height measurements will be performed.
- Adverse event reporting.

8.1.2. Visit 1

The following procedure will be completed at Visit 1. Details of the assessments are located in [Section 8.2](#):

- Record current medications.
- Record NYHA classification.

CCI

- Perform scintigraphy.
- Collect blood, and urine samples for the following clinical laboratories:
 - NT-Pro-BNP
 - Serum/urine test for primary (light chain) amyloidosis;
 - ATTR-CM biomarker samples;

- TTR genotyping.

CCI

- Adverse event reporting.

8.1.3. Follow-up 1 Visit

Participants will be informed of their diagnosis and collect any AE/RRI information within 14 days (+10 days) of study visit 1. This follow-up can be conducted remotely.

8.1.4. Follow-up 2 Visit

- Participants with scintigraphy of grade 1 or higher will be contacted to assess current medications and vital status. Participants with scintigraphy grade 1 will be asked if they have undergone a biopsy or other testing as follow up to scintigraphy since their last visit. Data will be collected on method of diagnosis and whether it confirmed the presence of ATTR-CM.

This post-study follow-up can be conducted remotely. This will occur 6 months after the Follow-up 1 Visit (+/- 30 days) or at early study discontinuation.

8.2. Assessments

8.2.1. Scintigraphy

All participants will undergo radionuclide cardiac scintigraphy at Visit 1 with a bisphosphonate radiotracer: ^{99m}Tc -DPD, ^{99m}Tc -PYP, or ^{99m}Tc -HMDP. Cardiac retention of all ^{99m}Tc -DPD, ^{99m}Tc -PYP, or ^{99m}Tc -HMDP will be determined by the central reader according to the grading:

Grade 0=absent cardiac uptake.

Grade 1=mild uptake less than bone.

Grade 2=moderate uptake equal to bone.

Grade 3=high uptake greater than bone.

Details of scintigraphy will be provided in a separate laboratory manual (Scintigraphy manual).

To confirm a diagnosis of ATTR-CM a participant with Grade 1 scintigraphy should undergo an endomyocardial biopsy.^{20,32} If biopsy or other confirmatory testing is performed, data will be collected.

8.2.1.1. Management of Incidental Findings from Scintigraphy

An incidental finding is one unknown to the participant that has potential health or reproductive importance, which is discovered unexpectedly in the course of a research study but is unrelated to the purpose and beyond the aims of the study.

Scintigraphy images will be reviewed by a central review facility. The purpose of this review is to evaluate images for diagnosis of ATTR-CM. Central image review is not a complete medical review of the participant. If, during the central review process, an unexpected observation is identified and this finding could, in the opinion of the central reviewer, have a significant health or reproductive consequence, this finding may be shared with the study sponsor for disclosure to the principal investigator (PI). All follow-up testing and final diagnosis will be left to the discretion of the medical professionals at the site or those with an existing physician-participant relationship. The PI will be responsible for reporting any adverse events (AEs) identified from incidental findings as described in the [AE reporting](#) section. Identification of such incidental findings during the central review process should not be expected, and the site maintains responsibility for performing a general safety review of all images as per site protocols.

8.2.2. Echocardiogram

Echocardiography (2D Doppler) will be performed and data collected for all participants at Screening unless one has been obtained within 6 months prior to Screening Visit and results are available. The assessment of end-diastolic interventricular septal thickness and left ventricular ejection fraction for study entry will be based on the echocardiogram performed at (or within 6 months prior to) the Screening visit as interpreted locally by the qualified reader (physician trained in echocardiography) at the site. If the Screening echocardiographic recording is not clear enough to accurately determine the end-diastolic interventricular septal wall thickness and left ventricular ejection fraction, it must be repeated. Each echocardiogram will be recorded and reviewed locally by the qualified reader at the clinical site, and the clinical significance of echocardiogram findings will be assessed by the investigator.

The following echocardiographic parameters should be collected if available:

1. End-diastolic interventricular septal wall thickness (mm).
2. End-diastolic left ventricular posterior wall thickness (mm).
3. Left ventricular ejection fraction (%).
4. Left atrial diameter, anterior-posterior (mm).
5. Left atrial diameter, medio-lateral (mm).
6. Left atrial diameter, superior-inferior (mm).
7. Left ventricular end systolic diameter (mm).

8. Left ventricular end systolic volume (mL).
9. Left ventricular end-diastolic diameter (mm).
10. Left ventricular end-diastolic volume (mL)..
11. E/A Ratio.
12. E/E' Ratio.

8.2.3. Cardiac Biomarkers: N-Terminal Pro-Hormone Brain Natriuretic Peptide (NT-proBNP) CCI

A 2.5 mL blood sample for NT-proBNP will be collected at Visit 1 and analyzed locally by the investigator site.

CCI

Specifications for sample collection can be found in the study laboratory manual.

8.2.4. Biospecimens for ATTR-CM Biomarker Identification and Validation

The following biospecimens for ATTR-CM biomarker research are required and will be collected from all participants in this study at Visit 1 as specified in the [SoA](#) (as allowed by local law):

- Collection of 56 mL blood including:
 - 2 K2EDTA plasma samples (10mL each),
 - 2 lithium heparin plasma samples (8mL each), and
 - 2 serum sample tubes (10mL each).
- Collection of 10 mL of urine.

Details on processes for collection and shipment of these samples can be found in the study laboratory manual.

8.2.5. TTR Genotyping

Participants will require collection of a 4 mL blood sample for potential TTR genotype testing, subject to local laws and regulations, at Visit 1. If the participant is diagnosed with scintigraphy grades 1, 2, or 3 then the sample will be sent to a reference laboratory for analysis and complete genomic sequencing of the TTR gene.

8.2.6. Testing for Light Chain Amyloid

Specifications for testing samples are provided in the study laboratory manual. Blood and urine specimens for serum free light chains assay and the serum and urine electrophoresis with immunofixation will be obtained from all participants, but only analyzed for those with scintigraphy Grades 1, 2, or 3. As standard of care, participants with serum or urine test result indicative of monoclonal gammopathy of undetermined significance (MGUS) will require a confirmatory biopsy performed locally.

8.2.7. Medical History

A complete medical history is to be documented for all participants at the Screening visit. This medical history will document the specific symptoms the participant reports associated with ATTR-CM, as well as any additional co-morbid conditions or symptoms including but not limited to:

- Sprains/strains.
- Transthyretin amyloid polyneuropathy (ATTR-PN).
- Arthroplasty.
- Pacemaker or implantable cardioverter defibrillator (ICD).
- Carpal tunnel syndrome.
- Biceps tendon rupture.
- Lumbar spinal stenosis.
- Achilles tendon rupture (nontraumatic).
- Rotator cuff injury (nontraumatic).
- Atrial fibrillation/Atrial flutter.
- Heart block.
- Intracardiac thrombus.
- Embolic stroke.

8.2.8. Vital Signs

Vital signs (including systolic and diastolic blood pressure, and pulse rate) will be assessed and recorded at the Screening visit. Orthostatic blood pressure changes will be measured with the participant's arm supported at the level of the heart and recorded to the nearest mm Hg. Rounding up to the nearest 5 or 10 mmHg is not permitted. The participant should be supine for at least 3 minutes before the supine blood pressure is obtained. Standing blood

pressure should then be measured approximately 2 minutes after the participant assumes the standing position.

The use of automated devices for measuring BP and pulse rate is acceptable, although when performed manually, pulse rate will be measured in the brachial/radial artery for at least 30 seconds.

When the timing of these measurements coincides with a blood collection, blood pressure and pulse rate should be obtained prior to the nominal time of the blood collection.

8.2.9. Medications

A list of current medications will be collected at Visit 1 for all participants; and Follow-up 2 Visit for participants with scintigraphy grade 1, 2 or 3.

CCI

8.2.11. NYHA Classification

The extent of participants' heart failure will be evaluated at Visit 1 using the New York Heart Association (NYHA) classification.

Class I: Participants with cardiac disease but without resulting limitations of physical activity. Ordinary physical activity does not cause undue fatigue, palpitation, dyspnea, or anginal pain.

[figure not shown]
Class II: Participants with cardiac disease resulting in slight limitation of physical activity. They are comfortable at rest. Ordinary physical activity results in fatigue, palpitation, dyspnea, or angina pain.

Class III: Participants with cardiac disease resulting in marked limitation of physical activity. They are comfortable at rest. Less than ordinary physical activity causes fatigue, palpitation, dyspnea, or anginal pain.

Class IV: Participants with cardiac disease resulting in inability to carry on any physical activity without discomfort. Symptoms of cardiac insufficiency or of the anginal syndrome may be present even at rest. If any physical activity is undertaken, discomfort is increased.

CCI

8.2.14. Physical Examination and Height and Weight Measurement

All participants will undergo a full physical examination at the Screening visit, including assessment of the following body systems:

General appearance	Neurological
Head and neck	Cardiovascular
Eyes	Abdomen
Ears	Skin
Nose	Musculoskeletal
Throat	Lungs
Genitourinary	

Measurement of height in centimeters (cm) or inches (in) and weight in kilograms (kg) or pounds (lbs.) will be performed at the Screening visit.

CCI

8.2.17. Vital Status

Participants, or their delegate, will be contacted at the Follow-up 2 Visit to determine vital status.

8.2.18. Subsequent Diagnosis of ATTR-CM

For participants who had scintigraphy grade 1 at Visit 1, information on subsequent diagnosis testing for cardiac amyloidosis and method thereof will be collected.

8.3. Safety

8.3.1. Adverse Events

An AE is any untoward medical occurrence in a patient or clinical study participant, temporally associated with the use of study intervention, whether or not considered related to the study intervention.

NOTE: An AE can therefore be any unfavorable and unintended sign (including an abnormal laboratory finding), symptom, or disease (new or exacerbated) temporally associated with the use of study intervention.

Any AE that occurs from the time the participant provides informed consent through and including up to 14 days following the participant's last visit must be recorded. The investigator is required to assess whether the AE may be related to the participant's participation in the study. All AEs (i.e., serious and non-serious, including those attributed to qualifying procedure identified as research-related injury) are collected in the clinical study database.

The investigator must pursue and obtain information adequate to determine the outcome of the AE and to assess whether it meets the criteria for classification as a research related injury requiring immediate notification to Pfizer as described below.

8.3.2. Research Related Injury

Should a participant, in the investigator's opinion, suffer a medically important research related injury caused by their participation in the study, the designated Pfizer clinician or medical monitor must be notified immediately.

A medically important research related injury is any untoward medical occurrence that:

- Results in death;
- Is life-threatening (immediate risk of death);
- Requires inpatient hospitalization or prolongation of existing hospitalization;

- Results in persistent or significant disability/incapacity (substantial disruption of the ability to conduct normal life functions);
- Results in congenital anomaly/birth defect.

Medical and scientific judgment is exercised in determining whether an injury is an important medical event. An important medical event may not be immediately life-threatening and/or result in death or hospitalization. However, if it is determined that the event may jeopardize the participant or may require intervention to prevent one of the other outcomes listed in the definition above, the important medical event should be reported as a research related injury.

An investigator may be requested by the designated Pfizer clinician or medical monitor to obtain specific additional follow-up information in an expedited fashion. In general, this will include a description of the injury in sufficient detail to allow for a complete medical assessment of the case and independent determination of possible causality. Information on other possible causes of the event, such as concomitant treatments, vaccines, and/or illnesses must be provided. In the case of a participant death, a summary of available autopsy findings must be submitted as soon as possible to Pfizer or its designated representative.

9. STATISTICAL CONSIDERATIONS

Detailed methodology for summary and statistical analyses of the data collected in this study will be documented and will be maintained by the sponsor.

The primary completion date (PCD) for the global prevalence estimate will be the date when all enrolled participants have either been diagnosed with ATTR-CM (scintigraphy grades 2 or 3), have scintigraphy grade 1 or found to be negative for ATTR-CM (scintigraphy grade 0) and have completed Follow-up Visit 1. Results will be reported after PCD and at the end of study (LPLV for participants with scintigraphy grade 1, 2 or 3).

The empirical estimate for the prevalence of ATTR-CM in HFpEF participants is approximately 10%. The study will enroll approximately 2000 HFpEF participants within whom it is expected to detect 200 ATTR-CM participants. Enrollment will be stopped if 200 ATTR-CM participants are identified before 2000 HFpEF are enrolled. No formal sample size calculation was performed. A sample size of 2000 HFpEF participants would be sufficient to inform treatment guidelines and yield an estimate for the global prevalence of ATTR-CM in HFpEF participants with a precision of $\pm 2.5\%$.

The primary endpoint is an estimate of the global prevalence of ATTR-CM in HFpEF participants. Diagnosis of ATTR-CM is defined as:

- Cardiac Scintigraphy Grade 1, with confirmation of ATTR by cardiac biopsy; or
- Cardiac Scintigraphy Grade 2 or above.

This global prevalence estimate will be obtained by dividing the number of participants who are diagnosed with ATTR-CM in the study by the total number of HFpEF participants evaluated. A 95% confidence interval on the estimate will also be calculated.

As secondary analysis, prevalence will be estimated for:

- Regions and countries.
- Age categories (60-64, 65-69, 70-74, 75-79, 80-85, >85).
- Gender (male, female).

Prevalence estimates along with 95% CI will be generated for regions and countries with at least 50 participants. For regions and countries that enroll fewer than 50 participants, prevalence will not be estimated. Regions will be defined in the statistical analysis plan. The proportion of HFpEF participants who were diagnosed with wild-type and variant ATTR-CM will be descriptively summarized.

As a general rule, the secondary endpoints other than the prevalence estimates and all CCI reported as numerical values will be analyzed descriptively using mean, standard deviation, median, minimum and maximum. Endpoints that are categorical will be summarized using frequency tables.

Analysis by Scintigraphy:

Participants who are diagnosed with ATTR-CM will be analyzed by scintigraphy grades (Grade 1, 2, or 3) using the 6-MWT, NT-proBNP, medical history, demographics (including age, TTR Genotype, gender and race), NYHA classification (Class I, II, III, or IV), and all CCI

Analysis by Disease Status:

Participants who are diagnosed with ATTR-CM will be analyzed by NYHA Classification (Class I, II, III, or IV) using the 6-MWT, NT-proBNP, medical history, demographics (including age, TTR Genotype, gender, and race) CCI

Participants who are diagnosed with ATTR-CM will also be analyzed by 6-MWT quartile groups using NYHA baseline classification (Class I, II, III, or IV), NT-proBNP, medical history, demographics (including age, TTR Genotype, gender, and race) CCI

Analysis Comparing ATTR-CM participants with HFpEF patients without ATTR-CM:

HFpEF participants diagnosed with ATTR-CM will be compared with HFpEF participants not diagnosed with ATTR-CM descriptively using medical history, demographics (including age, TTR Genotype, gender, and race) CCI

Medical history data will be used to generate descriptive statistics for time from symptom onset to HFpEF diagnosis and time from symptom onset to ATTR-CM diagnosis.

Endpoints measuring proportion of participants (NYHA Classification and symptoms of interest from medical history) will be compared between HFpEF participants diagnosed with ATTR-CM and those that are not diagnosed with ATTR-CM. The Chi-square test will be used to compare the proportions between these 2 groups of HFpEF participants. Fisher's exact test will be used instead of the chi-square test if any one of the cells has ≤ 5 participants. Secondary CCI endpoints that are normally distributed will be compared between 2 groups of HFpEF participants using a t-test. Endpoints that are not normally distributed will be compared using the Wilcoxon rank sum test.

Safety Analysis:

Adverse events (AEs) and research related injuries (RRI) collected at Visit 1 or during Follow-up visits, will be summarized overall and separately for HFpEF participants diagnosed with ATTR-CM and HFpEF participants not diagnosed with ATTR-CM.

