3.4. Baseline Variables

This study does not have a study treatment and all assessment for the primary, secondary, and CCI endpoints, are collected either during the Screening Visit or Visit 1 (Day 1).

CCI

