6. ANALYSES AND SUMMARIES

6.1. Primary Endpoint(s)

The primary endpoint is an estimate of the global prevalence of ATTR-CM in HFpEF participants. Diagnosis of ATTR-CM is defined as:

- Cardiac Scintigraphy Grade 1, with confirmation of ATTR by cardiac biopsy during the study period, or:
- Cardiac Scintigraphy Grade 2 or above.

The primary endpoint will be evaluated by dividing the number of participants who are classified as ATTR-CM positive by Cardiac Scintigraphy (as noted above) by the total number of HFpEF evaluable participants in the study. The proportion of Scintigraphy Grade 1 participants that are diagnosed with ATTR-CM will be estimated. Scintigraphy

Grade 1 participants that are diagnosed with ATTR-CM using a criteria other than cardiac biopsy and participants lost to follow-up without a confirmation of cardiac biopsy will be assumed as not diagnosed with ATTR-CM in the primary analysis. Exact 95% confidence intervals for the prevalence will be calculated using the method of Clopper and Pearson.¹ The primary analysis will be generated using the “Evaluable Analysis Set”.

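### The prevalence estimate at the primary completion date is taken at Follow-up 1, before the Grade 1 biopsy confirmations scheduled for Follow-up 2 are complete, so it can only err downward

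*Protocol*

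**What the plan says.** **Endpoint.** Besides Grade 2 or above, Protocol 9 counts this as a case: "Cardiac Scintigraphy Grade 1, with confirmation of ATTR by cardiac biopsy; or". SAP 6.1 adds a time limit: "Cardiac Scintigraphy Grade 1, with confirmation of ATTR by cardiac biopsy during the study period, or". Under Protocol 4.4 the study ends only when all applicable visits, including Follow-up 2, are complete.

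**When the information is collected.** Follow-up 1 is early: "Participants will be informed of their diagnosis and collect any AE/RRI information within 14 days (+10 days) of study visit 1". The confirmation question belongs to Follow-up 2. Protocol 8.1.4 states: "Participants with scintigraphy grade 1 will be asked if they have undergone a biopsy or other testing as follow up to scintigraphy". On timing it says: "This will occur 6 months after the Follow-up 1 Visit (+/- 30 days) or at early study discontinuation". The Schedule of Activities (SoA) marks subsequent diagnosis testing at Follow-up 2 only. Protocol 8.2.1 and 8.2.18 also say that confirmatory data will be collected, but name no visit.

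**When the estimate is reported.** Protocol 9 sets the PCD for the global prevalence estimate when every participant has a Grade 2 or 3 diagnosis, or "have scintigraphy grade 1 or found to be negative for ATTR-CM (scintigraphy grade 0) and have completed Follow-up Visit 1". Results are reported after PCD and again at end of study.

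**Counting rule.** SAP 6.1 treats Grade 1 diagnosed by criteria other than biopsy as not diagnosed. It adds: "participants lost to follow-up without a confirmation of cardiac biopsy will be assumed as not diagnosed with ATTR-CM in the primary analysis". SAP 5.3 allows no imputation.

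**Statement on data timing.** SAP 3.4 says of the assessments for the primary, secondary and further endpoints: "endpoints, are collected either during the Screening Visit or Visit 1 (Day 1".

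**The concern.** The date attached to the primary estimate comes before the visit that supplies part of the primary endpoint. The PCD definition lists Grade 1 apart from both diagnosed and negative, so a Grade 1 participant can be unresolved when the estimate is computed. SAP 6.1 has a rule for Grade 1 participants lost to follow-up but none for those still in follow-up.

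The stake is a first reported prevalence that may be lower than the end-of-study figure under the same definition, for no reason other than the data cut. Nothing says which of the two is the primary result, and Protocol 9 expects the estimate to inform treatment guidelines. The confidence interval does not reflect this error.

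Secondary results reported at PCD have the same gap. They use the SAP 6.1.1.1 definition, which also depends on Grade 1 diagnoses made after Visit 1. Pending Grade 1 participants would therefore sit in the comparison group without ATTR-CM.

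**Working it through.** **1. Timing.** Follow-up 1 falls at the latest 14 + 10 = 24 days after Visit 1. Follow-up 2 falls 6 months +/- 30 days after Follow-up 1. Taking 6 months as 182 days, that is 152 to 212 days later. Enrolment is staggered, so Grade 1 participants enrolled well before the PCD may already have had Follow-up 2. The gap concerns those enrolled in roughly the last 6 to 7 months.

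**2. Direction.** Let N be the evaluable participants, G the Grade 2-3 cases, C1 the Grade 1 biopsy confirmations recorded by the PCD, and C2 those recorded later. N and G are fixed at Visit 1 by scan evaluability and grade.

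- Estimate at PCD = (G + C1) / N
- Estimate at end of study = (G + C1 + C2) / N
- Difference = C2 / N, which is zero or positive

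**3. The plan's own figure.** 2000 x 10% = 200 expected cases, which reproduces. The exact (Clopper-Pearson) 95% CI for 200/2000 is 8.72% to 11.40%, a half-width of 1.34 points. This is narrower than the stated precision of +/-2.5%, so that precision is met and plays no part here.

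**4. What a shortfall would do.** Hold the end-of-study result at 200/2000 and vary C2. These values are assumptions.

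| C2 as share of the 200 cases | C2 | Estimate at PCD | Exact 95% CI |
|---|---|---|---|
| 0% | 0 | 10.0% | 8.72 to 11.40 |
| 2% | 4 | 9.8% | 8.53 to 11.19 |
| 5% | 10 | 9.5% | 8.25 to 10.87 |
| 10% | 20 | 9.0% | 7.78 to 10.34 |
| 20% | 40 | 8.0% | 6.85 to 9.28 |

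From C2 = 27 (173/2000 = 8.65%, upper limit 9.97%) the interval at PCD excludes 10%.

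**5. Illustration of C2.** C2 / N = Grade 1 share x share eventually biopsy-confirmed x share pending at PCD. The documents give none of the three. With uniform accrual over A months, the pending share is about min(1, 6/A): 50% for A = 12, 37.5% for A = 16, 25% for A = 24. This treats every confirmation as recorded at Follow-up 2 and none before.

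- Middle values: 5% x 30% x 37.5% = 0.56 points, or 2000 x 0.0056 = about 11 participants.
- Low values: 3% x 20% x 25% = 0.15 points.
- No outstanding confirmations: 0 points.

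**6. What bounds would show.** With the middle values and a final 10.0%, the lower bound at PCD is 10.0 - 0.56 = about 9.4%. All pending Grade 1 make up 5% x 37.5% = 1.9 points, so the upper bound is about 11.3%. The final figure lies between them.

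**The case against.** The strongest reply is that the plan already deals with this. Protocol 9 reports again at end of study, Protocol 4.4 includes Follow-up 2 in that end, and SAP 6.1 counts confirmations throughout the study period. Listing Grade 1 separately in the PCD definition suggests that the sponsor knew it would be unresolved, and SAP 7.1 openly plans interim reporting. All of this stands, and it limits the point to the figure reported at PCD. A reader might infer that the study's final prevalence is biased by the timing; the documents do not support that. What the reply does not supply is a label marking the PCD figure as provisional, or a statement of which report is primary.

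A reader might also infer that the SAP directs pending Grade 1 participants to be counted as negative. It does not. Its rule covers loss to follow-up and diagnosis by other criteria. Non-case status for pending participants follows only by default, from dividing cases by all evaluable participants with no imputation.

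Two softer points also stand. Because Protocol 8.2.1 and 8.2.18 name no visit, and Follow-up 2 may be brought forward at early discontinuation, some confirmations could be recorded before the scheduled Follow-up 2. And SAP 3.4 sits under a baseline heading and is partly redacted, so it may mean study-performed assessments only. It changes no calculation, but as written it does not fit the Follow-up 2 collection.

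**Conclusion.** The point holds for the PCD estimate. Following the stated PCD rule produces a prevalence that can be too low and cannot be too high relative to the end-of-study figure under the same definition. That direction needs only a fixed denominator and a fixed Grade 2-3 count.

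The size is unknown. The documents give no Grade 1 share, confirmation rate or accrual time. It may be small, because biopsy is no longer required and results are collected only if testing takes place. The illustrative 0.6 points is under half of the 1.3-point half-width.

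It is tempting to claim an undercount as large as 10% x 50% x 50% = 2.5 points. That would need biopsy-confirmed Grade 1 to contribute 10% x 50% = 5 points, half of the planned 10% prevalence, and nothing in the documents supports it. Nor do they show that the shortfall would exceed the sampling error.

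**What to change.** - **Protocol 9 and SAP 6.1:** name as the primary prevalence result the analysis run when all Grade 1 participants have completed or missed Follow-up 2.
- **Any estimate at the Follow-up 1 cut:** label it provisional and show it with bounds. The lower bound counts Grade 2-3 plus Grade 1 already biopsy-confirmed. The upper bound adds all Grade 1 participants whose confirmation status is still pending. Report the number pending.
- **SAP 3.4:** state that Grade 1 confirmation is collected after Visit 1, at Follow-up 2.

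The cost is wording and one bounded estimate; no new data are needed. The definitive figure comes about 6 to 7 months after the last Follow-up 1, while the provisional figure stays available for early reporting.
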